5.3 Secondary Efficacy Analyses

Secondary efficacy variables include the following:

- Geometric mean IELT up to weeks 2, 4, 6, 8 and 10 of the randomized period, respectively.
- Average (arithmetic mean) IELT up to weeks 2, 4, 6, 8, 10 and 12 of the randomized period, respectively

Interval-based geometric mean IELT and average IELT for week 4, 8 and 12 (ie, events between baseline and week 4, between week 4 and week 8, and between week 8 and week 12) will also be calculated from the above two as differences between periods.

All analyses on the secondary efficacy variables will not be window-based as indicated in Section 2.2. The target day for each time point, except for week 12, will be used to determine to which interval or period a certain event belongs to. For example, all events on or before week 10 target day, day 70, will be included for analyses with IELTs up to week 10, while all events between day 29 (inclusive) and day 56 (inclusive) will be included for analyses with IELTs between week 4 and week 8. Any event data collected on or after the week 12 target date of day 84 of the randomized period, and before the day 1 (treatment day) of the open-label period, if applicable, will be included in analyses related to week 12.

Comparisons will be made for each active BOTOX[®] dose level vs. placebo without multiplicity adjustment.

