7.3.2 Secondary Efficacy Analyses

[figure not shown]
The following key secondary efficacy variables will be analyzed using ANCOVA, with the treatment as factor and with baseline value as a covariate:

[figure not shown]
- log-transformed geometric mean IELT up to week 2, 4, 6, 8, and 10, respectively
- average IELT up to week 2, 4, 6, 8, 10, and 12, respectively

• interval-based geometric mean IELT and average IELT for week 4, 8, and 12 (ie, events between baseline and week 4, between week 4 and week 8, and between week 8 and week 12)

Responder analyses using the fold-change threshold of 3, 4, 5, 6, 7, and 8 in the geometric mean IELT will also be conducted.

In addition, geometric mean IELT at visits will be analyzed using a likelihood-based Z-score, as well as a bootstrap test for pair-wise comparisons between each active treatment group and the placebo (Zhou et al, 1997). Nonparametric analysis including, but not limited to the Wilcoxon rank-sum test will also be performed on the geometric mean IELT. Details will be provided in the statistical analysis plan.

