5.3.1 Secondary Efficacy Analysis

Summary statistics will be provided for each of the secondary efficacy variables. Change from baseline in log-transformed geometric mean IELTs and change from baseline in average mean IELTs will also be calculated and summarized.

Same ANCOVA model used in Section 5.2.1 will be used to the change from baseline in the log-transformed geometric mean IELT up to weeks 2, 4, 6, 8, and 10, respectively as well as change from baseline in interval-based log-transformed geometric mean IELT for weeks 4, 8

and 12, with treatment as the fixed effect, and log-transformed baseline geometric mean IELT as the covariate.

Summary statistics will be provided for average IELT as well as change from baseline in average IELT by timepoint. A similar ANCOVA model will be used on change from baseline in average IELT as well as the interval-based average IELTs: the model will have treatment as the fixed effect and the baseline average IELT as the covariate. Change from baseline in average IELTs up to weeks 2, 4, 6, 8, 10 and 12 and the interval-based change from baseline in average IELT for weeks 4, 8 and 12 will not be log-transformed prior to analyses.

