5.4 Other Analyses of Secondary Efficacy Variables

Nonparametric analysis using the Wilcoxon rank-sum test will be performed on the geometric mean IELT up to weeks 2, 4, 6, 8 and 10 as well as interval-based geometric mean IELT for weeks 4, 8 and 12, to compare each active BOTOX[®] dose level vs. placebo. Responder analyses described in 5.2.2 will also be carried out for geometric mean IELTs up to weeks 2, 4, 6, 8 and 10.

Treatment comparisons of each active BOTOX[®] dose level vs. placebo Geometric mean IELT up to weeks 4, 8 and 12 will also be performed using methods described in Zhou et al, 1997:

1. The likelihood-based Z-score test: the comparison between an active BOTOX[®] dose level *i* and placebo is evaluated by the statistic Z_i :

$$Z_{i} = \frac{\hat{\mu}_{i} - \hat{\mu}_{0} + \frac{1}{2}(S_{i}^{2} - S_{0}^{2})}{\sqrt{\frac{S_{i}^{2}}{n_{i}} + \frac{S_{0}^{2}}{n_{0}} + \frac{1}{2}(\frac{S_{i}^{4}}{n_{i} - 1} + \frac{S_{0}^{4}}{n_{0} - 1})}}$$

Where $\hat{\mu}_i$ and $\hat{\mu}_0$ are the sample mean of the log-transformed geometric mean IELT of dose level *i* and placebo, S_i^2 and S_0^2 are the sample variance of the log-transformed geometric mean IELT of dose level *i* and placebo, and n_i and n_0 are the sample size of dose level *i* and placebo, respectively.

Assuming that for each of the active dose level *i* and placebo, the geometric mean IELT are independently log-normally distributed with means M_i and M_0 , respectively, then Z_i tests the null hypothesis of $M_i=M_0$, and under the null hypothesis Z_i is approximately standard normal.

2. Bootstrap approach:

Let \overline{T}_i , \overline{T}_0 and $\overline{T}^{(i,0)}$ be the sample mean of the geometric mean IELT of the dose level i, placebo and the two groups combined, respectively. $T_k^{(i)} = T_{ik} - \overline{T}_i + \overline{T}^{(i,0)}$ and $T_j^{(0)} = T_{0j} - \overline{T}_0 + \overline{T}^{(i,0)}$ form a sample with common mean $\overline{T}^{(i,0)}$, where T_{ik} and T_{0j} are the geometric mean IELT for the kth patient in dose level i and the jth patient in the placebo group, for k=1, ..., n_i and j=1,..., n_0. Resample from them with replacement 2000 times, $Z_{i1}^{*(b)}$,..., $Z_{in_i}^{*(b)}$ and $Z_{01}^{*(b)}$,..., $Z_{0n_0}^{*(b)}$ for each b=1, ..., 2000. Compute

$$t_{b,i}^* = \frac{\overline{Z}_i^{*(b)} - \overline{Z}_0^{*(b)}}{\sqrt{\frac{\tau_i^{*(b)2}}{n_i} + \frac{\tau_0^{*(b)2}}{n_0}}}, \text{ for b=1,..., 2000.}$$

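### SAP 5.3 gives two incompatible rules for the interval-based IELT means, and subtracting cumulative means does not give the mean for weeks 4–8 or 8–12

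*SAP*

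**What the plan says.** SAP 5.3 lists two secondary variables. The first is "Geometric mean IELT up to weeks 2, 4, 6, 8 and 10 of the randomized period, respectively"; the second is the arithmetic mean up to weeks 2, 4, 6, 8, 10 and 12. Both are cumulative from treatment.

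The section then adds interval-based geometric and arithmetic means for weeks 4, 8 and 12, which "will also be calculated from the above two as differences between periods". The same sentence explains the intervals in terms of events. So does Protocol 7.3.2, which describes them as "events between baseline and week 4, between week 4 and week 8, and between week 8 and week 12" and mentions no subtraction.

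The next paragraph of SAP 5.3 says the target day "will be used to determine to which interval or period a certain event belongs to", and gives the example that "all events between day 29 (inclusive) and day 56 (inclusive) will be included for analyses with IELTs between week 4 and week 8". For week 12, events from day 84 until open-label day 1 are also included.

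Three analyses use the interval variables:

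- SAP 5.3.1 fits an ANCOVA to "change from baseline in interval-based log-transformed geometric mean IELT for weeks 4, 8" and 12.
- SAP 5.3.1 also fits an ANCOVA to the arithmetic version, where the "interval-based change from baseline in average IELT for weeks 4, 8 and 12 will not be log-transformed prior to analyses".
- SAP 5.4 applies the Wilcoxon rank-sum test to the cumulative geometric means "as well as interval-based geometric mean IELT for weeks 4, 8 and 12, to compare each active" dose level with placebo.

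**The concern.** The only variables the clause can refer to are the two cumulative means listed just above it. Read as written, it tells the programmer to form the week 4–8 value as the mean up to week 8 minus the mean up to week 4, and the week 8–12 value in the same way. That quantity measures how far the running mean moved. It is not the latency during the interval, and it conflicts with the day rule in the following paragraph.

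These two intervals are the planned analyses that separate later response from the first weeks, so they bear on durability. Under the subtraction rule the log ANCOVA loses every patient whose later latency does not exceed his own earlier cumulative mean. SAP 2.3 imputes no efficacy data, so those exclusions would depend on the outcome itself. The arithmetic-mean ANCOVA and the Wilcoxon test would still run and would return results for the wrong quantity.

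**Working it through.** The plan states no figure to reproduce here. The check is algebra followed by numerical illustrations. All latencies, the baseline of 35 s and the event counts below are assumptions; the algebra does not depend on them.

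**1. Day boundaries.** 4 × 7 + 1 = 29, 8 × 7 = 56, 10 × 7 = 70 and 12 × 7 = 84. These agree with the days in SAP 5.3, so the event-based rule is consistent in itself.

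**2. What subtraction produces.** Let the intervals 0–4, 4–8 and 8–12 have event counts n1, n2, n3 and arithmetic means m1, m2, m3. Let C4, C8 and C12 be the cumulative means.

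- C4 = m1, so the first interval is unaffected.
- C8 − C4 = (n1·m1 + n2·m2)/(n1 + n2) − m1 = n2(m2 − m1)/(n1 + n2), which is not m2.
- C12 − C8 = n3(m3 − C8)/(n1 + n2 + n3), which is not m3.

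The difference is zero when the effect is constant, and negative whenever the interval mean is below the preceding cumulative mean. The sign condition is the same for geometric means subtracted in seconds.

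**3. Illustrations with equal event counts.** For interval means a, b, c, the cumulative geometric means (GM) are a, √(ab) and (abc)^(1/3). The cumulative arithmetic means (AM) are a, (a+b)/2 and (a+b+c)/3.

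| Case | Cumulative means (s) | By subtraction | Interval mean |
|---|---|---|---|
| Constant, AM, BOTOX 90 s | 90, 90, 90 | 0 s and 0 s | 90 s and 90 s |
| Constant, AM, placebo 45 s | 45, 45, 45 | 0 s and 0 s | 45 s and 45 s |
| Rising, GM, weeks 4–8 | 50, 60 | 60 − 50 = 10 s | 60²/50 = 72 s |
| Falling, GM, weeks 4–8 | 90, 70 | 70 − 90 = −20 s | 70²/90 = 54.4 s |
| 60/180/150 s, GM, weeks 8–12 | 60, 103.9, 117.4 | 13.5 s | 150 s |
| 60/180/150 s, AM, weeks 8–12 | 60, 120, 130 | 130 − 120 = 10 s | 150 s |

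Change from the 35 s baseline:

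- Constant case: subtraction gives 0 − 35 = −35 s in both arms, where the interval means give 90 − 35 = +55 s and 45 − 35 = +10 s. The arm difference is 0 s instead of 45 s.
- Rising case: ln(10/35) = −1.25 instead of ln(72/35) = +0.72, so an improvement appears as a worsening.
- Falling case: the logarithm of −20 does not exist.

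**4. Unequal counts.** With 6, 4 and 2 events and interval means of 180, 120 and 60 s, the cumulative arithmetic means are 180, 156 and 140 s. Subtraction gives −24 and −16 s instead of 120 and 60 s.

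**5. Subtracting logs instead of seconds.** This avoids undefined logs but gives a ratio of cumulative means. For interval means of 60, 120 and 180 s with equal counts, the cumulative geometric means are 60, 84.85 and 109.03 s. The ratios are 84.85/60 = 1.414 and 109.03/84.85 = 1.285, not 120 s and 180 s.

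**6. What would recover the interval mean.** Cumulative means suffice only if they are weighted by event counts N: (N8·C8 − N4·C4)/(N8 − N4), on the log scale for the geometric mean. In step 4 this gives (10 × 156 − 6 × 180)/4 = 120 s and (12 × 140 − 10 × 156)/2 = 60 s. The SAP gives no such formula.

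**7. Missing ingredient.** The secondary list of geometric means stops at week 10. The week 12 value needed for a week 8–12 difference is not one of the two variables the clause refers to.

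**The case against.** The strongest reply is that the documents already show which rule applies. The sentence describes the intervals by events, the next paragraph assigns events by day, and Protocol 7.3.2 is event-based. SAP section 12 declares no deviations from the protocol. SAP 5.3.1 takes the log of the interval geometric mean, which makes sense only for a positive mean. The clause can also be read as a difference between sets of events (those up to week 8 less those up to week 4), and that agrees exactly with the day rule.

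This is probably the intent. But the clause says the values are calculated from the two listed variables, and those are means. The set reading is not what the words most naturally say, and a programmer should not have to choose between two rules in adjacent paragraphs.

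Three smaller objections have some force. The geometric mean up to week 12 does exist, within the primary variable in SAP 5.1, so its absence from the secondary list is a minor point. Zero or negative latencies would show up in the summary statistics required by SAP 5.3.1, so a wrong derivation might be caught. That protection fails where every difference is positive, as in the rising case and the 60/180/150 s case. Finally, the illustrations show what the subtraction rule would do if programmed; they do not predict this trial's data.

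**Conclusion.** The concern holds. Followed literally, SAP 5.3 yields values that are not the interval means for weeks 4–8 and 8–12, and in some patients no log value at all. In the assumed examples the subtracted value is 0 s instead of 90 s or 45 s, 10 s instead of 72 s, −20 s instead of 54.4 s, and 13.5 s or 10 s instead of 150 s. The size of the error depends on the assumed latencies and event counts. That the difference of cumulative means is not the interval mean does not.

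The scope is narrow: two later intervals of secondary variables in an exploratory study, and only if the subtraction clause is the one programmed. The primary variable and the baseline-to-week-4 interval are unaffected. It should be corrected before the interval variables are programmed.

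**What to change.** In SAP 5.3, delete the clause that derives the interval values as differences of the cumulative variables. State instead that the geometric and arithmetic mean IELT for each interval are calculated directly from the evaluable events dated in that interval.

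State the boundaries for the later intervals: days 29 to 56 for weeks 4–8, and day 57 onward for weeks 8–12, ending before open-label day 1 where applicable. Day 57 is not written in the SAP but follows from day 56 being included in the earlier interval. Keep the log change from baseline for the geometric mean only, as SAP 5.3.1 already has it.

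The cost is one SAP sentence. The event-level diary data are already collected, and the primary analysis does not change.

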3.3 Open Label Period (Cohort 6)

At week 12, during the randomized period exit visit, patients who complete the double-blind period of the study will be eligible to enroll into the open-label period of the study.

The patient must complete the double-blind portion of the study and have received the first injection at least 12 weeks prior before receiving the second injection in the open-label period. Day 1 of the open-label period may occur on the same day as the week-12 visit of the randomized period (provided the 1st injection occurred at least 12 weeks prior) and may occur up to 4 weeks following the week-12 visit of the randomized period, provided all inclusion/exclusion criteria are met on the day of treatment.

If the Week 12 exit visit of the randomization period and the Day 1 treatment visit of the open-label period do not occur on the same day, the assessments of the Week 12 exit visit of

the randomization period should not be repeated at the Day 1 treatment visit of the open-label period, with the exception of recording AEs, concomitant medications/procedures, and vital signs.

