3.3.2 Day 1 of Open-Label Period Injection

Day 1 of the open-label period may occur on the same day as the week-12 visit of the randomized period (provided the 1st injection occurred at least 12 weeks prior) and may occur up to 4 weeks following the week-12 visit of the randomized period, provided all inclusion/exclusion criteria continue to be met on the day of treatment. Week 12 exit assessments of the randomization period should not be repeated at the Day 1 treatment visit of the open-label period, with the exception of recording AEs, concomitant medications/procedures, and vital signs.

4. Study Population and Entry Criteria

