6.3.4 Intravaginal Ejaculatory Latency Time

Patients will document sexual activities in the SID during screening and for 12 weeks following treatment to provide baseline and posttreatment IELT data.

Either the patient or female partner may operate the stopwatch, although the preference is for the female partner to operate the stopwatch. The stopwatch operator must be consistent throughout screening and the posttreatment period.

In the SID, patients will be asked to record the date and start time of each sexual encounter, the duration of intercourse (ie, the time from vaginal penetration until ejaculation, measured with a stopwatch), and a description of when the ejaculation occurred (ie, prior to penetration, intravaginal, did not occur, or after withdrawal) for all sexual intercourse attempts.

Patients must be instructed:

- that any behavioral techniques that were performed prior to screening should also be continued consistently for the duration of the study
- that the patient and female partner must not significantly alter their normal sexual practices during the course of the study (eg, amount of foreplay, use of lubrication, or position).
- that condoms must not be used during the study
- not to withdraw the penis from the vagina during intercourse as this would make the event nonevaluable
- to record all sexual intercourse events that constitute an attempt at penile penetration of the vagina, including any ejaculation that occurs before, during, or after the act of vaginal penetration
- that if ejaculation does not occur during intercourse and a new vaginal penetration is attempted, these separate vaginal penetrations must be recorded on the SID as 2 separate events

Additional study site instructions regarding the SID are provided in Attachment 12.2.

Sexual events recorded on the SID will be reviewed by the site and/or Allergan (or designee) to determine if the events are evaluable.

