12.2 Sexual Intercourse Diary

The SID will be completed by the patient and/or their female partner after any vaginal sexual activity during the screening visit and for 12 weeks following study treatment.

Study sites should adhere to the following general instructions:

- at each clinic visit, the SID is collected and reviewed for completeness and not content by the study site personnel in the patient's presence. Study site personnel will verify that all corrections made by the patient are initialed/dated by the patient. Study site personnel should not change information on the diary.
- review of SID is to occur after completion of questionnaires
- if information is not completely filled out in the diary, the patient/female partner should not be asked to recall the information
- instruct patients to refrain from altering their sexual activities (see Section 4.6) and refrain from condom usage (see Section 4.5.1.1)
- at the screening visit and each posttreatment clinic visit, the collected SID is filed as source document at the site
- completed only by the patient and/or female partner (no other outside influences such as family or study personnel)
- initialed and dated by the patient completing the diary
- completed for all attempted vaginal intercourse events
- completed only for vaginal intercourse events
- patient/female partner should call the site with any questions concerning completion of SID

[figure not shown]
Study sites should adhere to the following instructions during the screening period:

[figure not shown]
- provide initial stopwatch and SID training during the screening visit
- remind patient not to begin recording IELT in SID until after 28 days of washout has been completed (if applicable)
- instruct patients to provide at least 4 evaluable events (in a maximum of 28 days) during screening collection period

Study sites should adhere to the following instructions posttreatment:

- at the treatment visit and at each posttreatment clinic visit, SID and stopwatch training should be provided, as applicable, with emphasis on addressing corrective actions on any errors that were noted during SID review
- remind patient to wait at least 48 hours after treatment before engaging in vaginal intercourse
- instruct patients to aim for a minimum of 4 vaginal intercourse events per month for the duration of the study. For the open-label portion of the study, no minimum number of events per month is needed.

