4.5 Past Medical History

Medical history with onset dates prior to the informed consent date will be tabulated and presented for each treatment group and overall. Medical history will be coded using MedDRA primary system organ class (SOC). All medical history will be presented by

treatment group and overall. No statistical comparisons will be performed. A patient-level listing of medical and surgical histories will also be provided for each treatment group.

Patients are also asked to fill out a sexual history CRF which will record their PE therapy or techniques together with start/stop date information. The un-coded therapy/technique will be tabulated with number and percent of patients using each therapy/technique by treatment group and overall. A patient-level listing of the information collected will also be presented.

5. Efficacy Analyses

5.1 Collection of Primary Efficacy Measurement(s) and Derivation of Primary Efficacy Variable(s)

The primary efficacy measurement is the patient's IELT (second) collected from the Sex Intercourse Diary (SID). The SID will be completed by the patient and/or their female partner after any vaginal sexual activity during the screening visit and for 12 or 24 weeks following study treatment. Only IELTs from evaluable events recorded in the SID will be used for analyses.

An evaluable event is defined as:

• An event in which the patient and his partner had vaginal intercourse, and the couple have recorded that the ejaculation occurred "intravaginally" and duration of the time from penetration to ejaculation has been recorded

OR

• An event in which the patient and his partner attempted to have vaginal intercourse. However, the couple have recorded that ejaculation occurred "prior to vaginal penetration". In this scenario, the duration of time will be recorded as zero.

Any other scenarios will not be considered as evaluable and will not be included in deriving the primary efficacy variable, although time to withdrawal can be used in exploratory analyses. Number of evaluable events will be summarized by treatment group at baseline, weeks 2, 4, 8 and 12 for the randomized period of the study.

The primary efficacy variable is the change from baseline in logarithm value of the individual patient's geometric mean IELT for the entire 12 weeks of the randomized period of the study.

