For baseline, the geometric mean IELT is calculated from the most 4 recent evaluable events prior to study medication administration. The geometric mean of the IELTs from all postbaseline evaluable events up to week 12 is then calculated and the difference in the logarithm of the two geometric mean IELTs (postbaseline - baseline) will be calculated.

For IELTs that are zero (events in which ejaculation occurred prior to vaginal penetration), 0.5 (second) will be added for the calculation of geometric means.

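### For Cohort 6 patients who defer open-label treatment, SAP 5.3 lets the week-12 secondary IELT analyses run to the second injection, about 16 weeks at most

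*SAP*

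**What the plan says.** SAP 5.3 assigns diary events to periods by study day: "The target day for each time point, except for week 12, will be used". Its examples close on fixed days: week 10 on day 70, and the week 4-8 interval on days 29 to 56. Week 12 is handled differently. Events on or after day 84 and "before the day 1 (treatment day) of the open-label period, if applicable, will be included in analyses related to week 12". The same section says that these analyses do not use visit windows.

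Protocol 3.3 and 3.3.2 allow the open-label injection on the day of the week-12 visit, or it "may occur up to 4 weeks following the week-12 visit of the randomized period". Only Cohort 6 has an open-label period.

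The week-12 secondary variables are average IELT up to week 12 and the week 8-12 interval means, geometric and arithmetic. SAP 5.4 also applies a likelihood-based Z-score test and a bootstrap test to geometric mean IELT up to week 12.

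The primary variable is defined separately in SAP 5.1, from "all postbaseline evaluable events up to week 12", with no day number.

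The diary period is described inconsistently:
- Protocol 6.3.4: "for 12 weeks following treatment to provide baseline and posttreatment IELT data".
- Protocol Attachment 12.2: "for 12 weeks following study treatment".
- Protocol 6.3.4.3: recording continues until study exit.
- SAP 5.1: "for 12 or 24 weeks following study treatment".

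**The concern.** For a patient who defers, the end of a nominally 12-week endpoint is set by the date of an elective second injection. That date depends on facts arising after randomization: scheduling, patient choice, and the requirement in protocol 3.3.1 that the patient be free of ejaculatory adverse events. Two patients given the same dose can then contribute different lengths of follow-up to a variable with one name.

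The difference does not fall evenly across the comparison. SAP 2.3 pools placebo across cohorts, and 10 of the 22 planned placebo patients come from Cohorts 1-5, which have no open-label wait. The week 8-12 interval is the most exposed, because a full wait can double its length. It is also the interval that would show whether an effect lasts. If the effect fades after week 12, gap events would dilute it.

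**Working it through.** **1. Target days.** Target day = 7 × week gives 56, 70 and 84 for weeks 8, 10 and 12. These match the days in SAP 5.3, so nothing in the SAP is miscalculated.

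**2. Longest span.** The injection is on day 1, so a week-12 visit falls nominally on day 84 or 85. Adding the 28-day maximum puts open-label day 1 on day 112 or 113, and the last included day is 111 or 112.
- Up to week 12: 111-112 days (15.9-16.0 weeks) instead of 84.
- Week 8-12 interval, starting on day 57: 55-56 days instead of 28.
- With a day-85 visit, waits of 7 and 14 days give 13 and 14 weeks, and same-day treatment gives 12.

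**3. Share of data from the gap.** Assume 4 evaluable events per 28 days up to day 84, the minimum that protocol 6.3.4.3 asks couples to aim for. That gives 12 events up to week 12, of which 4 fall in the interval. No document sets a rate for the gap, so let g be the number of gap events. The share is g/(12+g) up to week 12 and g/(4+g) in the interval.

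| g | Up to week 12 | Week 8-12 interval |
|---|---|---|
| 0 | 0% | 0% |
| 1 | 7.7% | 20% |
| 2 | 14.3% | 33.3% |
| 4 | 25% | 50% |

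**4. Effect on one deferring patient.** Take a 4-fold effect up to day 84, and let w be the fraction of the log effect lost in the gap.
- Interval geometric mean = 4^(1 − share × w). For w = 0, 0.5 and 1: with g = 1 it is 4.00, 3.48 and 3.03-fold; with g = 4 it is 4.00, 2.83 and 2.00-fold.
- Average IELT up to week 12, in units of baseline, with gap events at 4, 2 or 1 times baseline: g = 1 gives 52/13 = 4.00, 50/13 = 3.85 and 49/13 = 3.77; g = 4 gives 64/16 = 4.00, 56/16 = 3.50 and 52/16 = 3.25.

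**5. Power for the interval geometric mean.** The method is that of protocol 7.5: a two-group t-test on logs, one-sided 0.10, SD = √ln(1 + CV²). With CV 1.5 the SD is √ln 3.25 = 1.086. At 12 versus 12 this gives 60.0% for a 2-fold and 87.5% for a 3-fold effect, against 60% and 88% in Table 7-1.

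The planned comparison is 12 BOTOX versus 5 × 2 + 12 = 22 pooled placebo. For a 2-fold effect the noncentrality is 0.693/(1.086 × √(1/12 + 1/22)) = 1.779 on 32 df, and power is 68.2%. If a fraction p of BOTOX patients defers, the mean log effect becomes ln 2 × (1 − p × share × w). For g = 1, p = 25%, this is 0.693 × 0.975 = 0.676 with half waning and 0.693 × 0.95 = 0.658 with full waning.

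| Gap events per deferring patient | Waning | p = 25% | p = 50% | p = 100% |
|---|---|---|---|---|
| 0, or any number with no waning | – | 68.2% | 68.2% | 68.2% |
| 1 | half | 66.7% | 65.1% | 61.7% |
| 1 | full | 65.1% | 61.7% | 54.9% |
| 4 | half | 64.2% | 60.1% | 51.4% |
| 4 | full | 60.1% | 51.4% | 34.3% |

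The model holds placebo at no effect and ignores any precision gained from extra events. It also assumes that the Cohort 6 dose group is the 12 patients of that cohort. The doses are blacked out. If an earlier cohort used the same dose, the group would be 20 (12 + 8) and the dilution smaller.

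**The case against.** The strongest objection is that gap data may barely exist. Protocol 6.3.4 and Attachment 12.2 limit the diary to 12 weeks, and Attachment 12.2 has it collected at each clinic visit. Protocol 3.3.2 adds that "Week 12 exit assessments of the randomization period should not be repeated at the Day 1 treatment visit of the open-label period", apart from adverse events, concomitant medications or procedures, and vital signs. The SAP's 12 or 24 weeks, and the study duration of up to 24 weeks, fit 12 + 12 with no wait; a full wait makes 12 + 4 + 12 = 28. This stands as a reason to expect few gap events, but it does not remove the rule. Protocol 6.3.4.3 keeps the diary going until exit, Attachment 12.2 mentions intercourse events in the open-label portion, and SAP 5.3 itself provides for events after day 84.

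A second objection is that the rule is sensible: it keeps valid events when the week-12 visit runs late, and it stops before re-treatment. That is right, and a strict day-84 cut would lose those events. It does not justify tying the end of the period to an elective injection date.

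A reader might infer more than the documents support:
- *That patients who never enter open label have no closing day.* SAP 5.3 gives them no day number, but week 12 is their exit visit and protocol 6.3.4.3 ends recording at exit.
- *That the primary variable also runs to 16 weeks.* The rule sits in the secondary section, and SAP 5.1 and protocol 7.2.1 tie the primary to the 12 weeks of the randomized period. The phrase about analyses related to week 12 leaves a doubt worth closing, not a demonstrated effect.
- *That the result is biased in a known direction.* Cohort 6 is randomized 1:1 and blinded, and both arms follow the same rule. An ejaculatory adverse event adds gap data only if it resolves within 4 weeks and the patient then elects treatment. The direction cannot be derived.
- *That power could halve.* The 34% figure needs every BOTOX patient to wait the full 4 weeks, record 4 gap events and lose all effect at day 84. Protocol 1.5 expects an effect lasting several months.

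**Conclusion.** The point holds in a limited form. For Cohort 6 patients who defer open-label treatment, average IELT up to week 12, the week 8-12 interval means and arguably the week-12 tests in SAP 5.4 can include events to about day 112, with an interval of about 56 days instead of 28. Cohorts 1-5, patients who do not continue and patients re-injected on the day of the week-12 visit are bounded by that visit.

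The effect is nil with no gap events or no waning. With one gap event per deferring patient and 25% of BOTOX patients deferring, the loss for a 2-fold interval effect is about 1.5 to 3 power points. It is larger only in upper-end cases. These sizes rest on assumed event rates, CV 1.5 and 12 versus 22 patients. This is an endpoint-window rule, not an arithmetic error. In an exploratory pilot with an empirical sample size it is of minor severity.

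**What to change.** Before database lock, close all week-12 efficacy analyses by one rule for every patient: a fixed study day that allows for a late week-12 visit, such as the upper limit of the week-12 visit window, and always before the open-label injection. State in SAP 5.1 that the same cut applies to the primary variable. List events after the cut separately, and keep the current SAP 5.3 rule as a sensitivity analysis.

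The cost is one changed rule and one extra run, with no new data, visits or patients. The downside is that a few late randomized-period events leave the main analysis.
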